## Statement of Compliance

This study will be conducted in accordance with the International Conference on Harmonisation guidelines for Good Clinical Practice (ICH E6), the Code of Federal Regulations on the Protection of Human Subjects (45 CFR Part 46), and Thomas Jefferson University research policies

## List of Abbreviations

AE	Adverse Event/Adverse Experience
CFR	Code of Federal Regulations
CIOMS	Council for International Organizations of Medical Sciences
CONSORT	Consolidated Standards of Reporting Trials
CRF	Case Report Form
CRO	Clinical Research Organization
CTCAE	Common Terminology Criteria for Adverse Events
CTSQ	Cancer Treatment Satisfaction Questionnaire
DSMC	Data and Safety Monitoring Committee
DSMP	Data and Safety Monitoring Plan
FDA	Food and Drug Administration
FWA	Federalwide Assurance
GCP	Good Clinical Practice
GWAS	Genome-Wide Association Studies
HIPAA	Health Insurance Portability and Accountability Act
IB	Investigator's Brochure
ICF	Informed Consent Form
ICH	International Conference on Harmonisation
IDE	Investigational Device Exemption
IND	Investigational New Drug Application
IRB	Institutional Review Board
MedDRA	Medical Dictionary for Regulatory Activities
MOP	Manual of Procedures
N	Number (typically refers to participants)
NCI	National Cancer Institute
NIH	National Institutes of Health
OHRP	Office for Human Research Protections
OOCAT	Oncology Opportunity Cost Assessment Tool
PHI	Protected Health Information
PI	Principal Investigator
PRC	Protocol Review Committee
QA	Quality Assurance
QC	Quality Control

SAE	Serious Adverse Event/Serious Adverse Experience
SDS	Safety Data Sheet (formerly MSDS; Material Safety Data Sheet)
SKCC	Sidney Kimmel Cancer Center
SOP	Standard Operating Procedure
TJU	Thomas Jefferson University
UAP	Unanticipated Problem

## Study Summary

Title:	Open Label Single Arm Study to Assess the Implementation of Home based daratumumab administration.
Précis:	This study will include all patients on the monthly phase of daratumumab. Patient reported outcome metrics as well as implantation metrics will be measured.
Objectives:	
Primary: Evaluate treatment burden (using the CTSQ).
 
Secondary:
 

1. Determine adherence to home delivery of Darzalex-Faspro.

2. Evaluate quality of life (using EORTC QLQ-30) based on site of care (home vs. infusion center).

3. Evaluate financial burden (using the COST survey) based on site of care (home vs. infusion center).

4. Evaluate Safety of home administration of darzalex-faspro.

5. Evaluate barriers to home administration.

 
Exploratory:
 

1. Evaluate patient perceptions of home administration of anti-neoplastic therapy

2. Evaluate opportunity cost based on site of care (home vs. infusion center) using the Oncology Opportunity Cost Assessment Tool (OOCAT)

Population:	The sample size will be 20 participants. All patients with a diagnosis of multiple myeloma who are receiving the monthly phase of daratumumab.
Phase:	Pilot study
Number of Sites:	1- Sidney Kimmel Cancer Center Thomas Jefferson University [name]

**Description of Intervention:**

- 1) All participants included in the study will receive daratumumab subcutaneous injection therapy (fixed dose 1800mg). On study, participants will receive 2 cycles of daratumumab in the infusion center, followed by 4 cycles at home followed by 2 more cycles at the infusion center. At the beginning of each cycle, patient reported outcome surveys and quality of life surveys will be collected (EORTC-QLQ-30, CTSQ, COST, and OOCAT). During the infusion center phase, administration will be given by an infusion center nurse. During the home infusion phase of the study a home infusion nurse will administer darzalex-faspro. During home administration, specific details on barriers to maintaining adherence will be collected and described with descriptive analysis (i.e. issues with storage, delivery, disposal of medication).

**Study Duration:** 36 months

**Participant Participation Duration:** 10 months

**Estimated Time to Complete Enrollment:** 26 months

## Schematic of Study Design:

### Screening Visit

Total N: 20. Obtain informed consent. Screen potential subjects by inclusion and exclusion criteria; obtain medical history, prior/comcomitant medications, adverse event assessment, physical exam, ECOG, score, Baseline labs as per SOC (CBC, CMP).

Arm 1: On monthly  
Daratumumab

### Visit 1-2 C1D1 C2D1

Physical Exam, ECOG assessment, AE assessment  
Labs: CBC, CMP, SPEP/IFE, Serum Immunoglobulins, Serum Free Light Chains, Surveys: CTSQ, EORTC QLQ-30, COST survey, OOCAT (To be performed 3-5 days after the visit)

### Visit 3-6 C3D1 C4D1 C5D1 C6D1

Limited Physical Exam (may be virtual), ECOG assessment, AE assessment  
Labs: CBC, CMP, SPEP/IFE, Serum Immunoglobulins, Serum Free Light Chains, Surveys: CTSQ, EORTC QLQ-30, COST survey, OOCAT (To be performed 3-5 days after the visit)  
Perform Barrier Assessment to home infusion

### Visit 7-8 C7D1 C8D1

Physical Exam, ECOG assessment, AE assessment  
Labs: CBC, CMP, SPEP/IFE, Serum Immunoglobulins, Serum Free Light Chains, Surveys: CTSQ, EORTC QLQ-30, COST survey, OOCAT (To be performed 3-5 days after the visit)

### Visit 9 No later than 45 days After C8D1

Perform Semi-structured  
qualitative interview  
AE Assessment

## 1 Introduction

### 1.1 Background Information

Multiple myeloma is an incurable cancer of the plasma cells that can be complicated by hypercalcemia, renal failure, anemia, bone lesions, and recurrent infections. Over the last two decades the treatment paradigm for multiple myeloma has changed dramatically[1]. With the evolution of more effective treatments, patients are living longer with a better quality of life. As

part of this evolution, especially within the US, continuous treatment approach as opposed to intermittent treatment approach has become the standard of care[2]. However, these improvements come with a cost. Not only is the total cost of care extraordinary[3-5], but the financial burden on the patient is also high[6]. In one study, 46% of patients with a diagnosis of multiple myeloma had to use their savings to help pay for their cost of care and 71% experienced financial burden with 20% of respondents reporting severe financial burden[6].

In addition, to financial cost of care, treatment burden and exposure to the healthcare system must be considered. For many patients receiving anti-myeloma therapy, treatments require weekly visits to the cancer center resulting in hours of time spent traveling to, waiting for, and receiving treatment. Time that could be spent in the comfort of their homes. This is particularly important in the current pandemic, in which patients are encouraged to shelter in place in order to minimize exposures to SARS-CoV-2. A recent study published revealed that patients with multiple myeloma, regardless of their disease status, have a high mortality rate if they contract SARS-CoV-2[7]. As a result of this publication and other data, the American Society of Hematology continues to recommend minimizing patient exposure to the health care system and to consider changing to all oral therapy when able[8]. While this recommendation balances efficacy of treatment with risk of COVID-19, treatment efficacy is compromised as it has been well established that triplet or quadruplet (if dara containing regimen) is superior to doublet therapies [9-11].

For these reasons mentioned above, home-based chemotherapy, administered by a trained team, should be considered. Chemotherapy at home remains uncommon in the US, though models for its use exist globally[12]. In these models, home-based chemotherapy is safe, preferred by patients, and can be administered at lower cost. Given that the healthcare economics within the United States is not comparable to other systems where a national healthcare system exists, research into the implementation of and barriers to home based chemotherapy within the US is vital. This need is reinforced by a recent position statement published by ASCO[13]. Herein, we propose to evaluate the implementation of a home based subcutaneous daratumumab program for patients with multiple myeloma. We hypothesize that this program will be feasible, reduce patient treatment and financial burden, improve quality of life and at the same time, minimize risk to the patient during the COVID-19 pandemic without sacrificing treatment efficacy.

## 1.2 Rationale for the Proposed Study

We propose to study the implementation of a home based anti-neoplastic therapy program with subcutaneous daratumumab and hyaluronidase-fihj (1800mg fixed dose). Home based chemotherapy has been well established in countries with national health care systems, but it has not been well studied within the US healthcare system. We plan to evaluate patient reported outcomes related to quality of life, treatment burden and cost burden of a home based anti-neoplastic therapy model. We will also evaluate the feasibility of delivering and administering anti-neoplastic therapy in the home. We

---

hypothesize that a home based anti-neoplastic therapy program will be feasible and improve quality of life while at the same time reduce treatment and cost burden.

### 1.3 Correlative Studies

N/A

### 1.4 Potential Risks and Benefits

#### 1.4.1 Potential Risks

Potential risks associated with the administration of DARZALEX FASPRO in the home:

- Potential for delay in treatment due to medication not being delivered.
- Potential for missed doses or wasted doses of medication.

#### 1.4.2 Benefits

Potential benefits of the study include:

- Improved quality of life while receiving medication in the home setting
- Decreased cost of care during the study period
- Decreased burden of care during the study period

## 2 Study Objectives

### 2.1 Objectives

#### 2.1.1 Primary

1. Evaluate treatment burden (using the CTSQ).

#### 2.1.2 Secondary

1. Determine adherence to home delivery of DARZALEX FASPRO.
2. Evaluate quality of life (using EORTC QLQ-30) based on site of care (home vs. infusion center).
3. Evaluate financial burden (using the COST survey) based on site of care (home vs. infusion center).
4. Evaluate Safety of home administration of darzalex-faspro.
5. Evaluate barriers to home administration.

### **2.1.3 Exploratory**

1. Evaluate patient perceptions of home administration of anti-neoplastic therapy.
2. Evaluate opportunity cost based on site of care (home vs. infusion center) (using the OOCAT survey).

## **2.2 Endpoints/Outcome Measures**

### **2.2.1 Primary**

1. Treatment satisfaction will be measured using the Cancer Treatment Satisfaction Questionnaire (CTSQ).

### **2.2.2 Secondary**

1. Adherence is defined as completing administration of medication in the home setting. Adherence will be measured for each dose given and failure would occur if the participant needs to go to the infusion center for administration for whatever reason. Based on previous studies of home based administration adherence rates over 75% would be needed to meet criteria for feasibility.
2. Measurement of quality of life will be measured using the EORTC QLQ-30.
3. Financial toxicity will be measured using the COST survey.
4. Safety will be evaluated through collection of adverse events, administration reactions related to Darzalex-Faspro.
5. Barriers to home administration will be measured through any delays in treatment related to delivery of medication, arrival time of the infusion nurse, issues related to storage of medication, issues related to administration of the medication.

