### 11.2 Analysis Plans

For primary analysis, the SWT domain CTSQ scores after all cycles will be analyzed jointly in a linear mixed effects model with a random effect of patient and the fixed effect of the delivery mode (home vs. infusion center). Log or other transformation of CTSQ scores will be used, as appropriate, to satisfy the model assumptions. Possible time trends will be considered in the model and incorporated, if significant. The mean difference in CTSQ scores between home and infusion center will be computed with the corresponding 95% confidence interval and tested (null hypothesis of zero mean difference) using appropriate model-based contrast with alpha 0.05.

The same approach will be used for the secondary analysis of other CTSQ domains, EORTC QLQ-30, COST survey, and OOCAT survey scores.

The adherence at the home setting cycles will be analyzed in repeated measures logistic regression model with a random effect of patient and the fixed effect of the delivery mode (home vs. infusion center). The model will be used to compute the average rate of home setting adherence with the corresponding 95% confidence interval.

---

Secondary endpoints related to the barriers to home administration and exploratory endpoints related to the patient perceptions of home based anti-neoplastic therapy will be summarized using descriptive statistics.

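### Followed literally, the adherence rule leaves out scheduled home doses that are never given, which raises the crude rate set against the 75% feasibility bar

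*Combined protocol and SAP*

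**What the plan says.** Section 2.2.2, secondary endpoint 1, opens with a definition: "Adherence is defined as completing administration of medication in the home setting". The next sentence gives the counting rule, under which adherence is "measured for each dose given and failure would occur if the participant needs to go to the infusion center for administration for whatever reason". The item closes with the criterion that "adherence rates over 75% would be needed to meet criteria for feasibility".

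Section 11.2 says "The adherence at the home setting cycles will be analyzed in repeated measures logistic regression model", with a random patient effect, and adds: "The model will be used to compute the average rate of home setting adherence", with a 95% confidence interval. It does not state the denominator, or how a home cycle with no dose is scored.

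Three other places bear on the point:
- The Study Summary sets the schedule: two infusion-center cycles, "followed by 4 cycles at home followed by 2 more cycles at the infusion center".
- Section 1.4.1 lists as a risk of home delivery: "Potential for missed doses or wasted doses of medication". Section 5.4 also allows doses to be withheld.
- Section 4.4.2 returns participants who stop early to the infusion center and allows them to be replaced.

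**The concern.** The definition and the counting rule disagree on one foreseeable case. A scheduled home dose that is never given has not been completed at home, so it fails the definition. Under the counting rule it is not a dose given, and the single failure event named, a move to the infusion center, has not happened. It therefore drops out of both numerator and denominator.

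This works in the wrong direction for a feasibility measure. A home programme that fails to deliver a dose at all would score better than one that reroutes the patient and gets the dose in. In Section 1.2 the investigators "hypothesize that a home based anti-neoplastic therapy program will be feasible", and the 75% figure is the only numeric criterion for that. The study is open label, so while the denominator is unstated, the choice between the two readings could be made after the counts are known.

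**Working it through.** **The plan's own figures.** The only figure for adherence is the 75% bar, and no calculation lies behind it that could be reproduced. The only computed figure in Section 11 is the primary endpoint's 80% power. It reproduces (exact paired-t power 0.801 with n = 20, difference 5.9, SD 8.92, two-sided alpha 0.05) and does not depend on adherence.

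**Inputs.**
- Participants: 20 (Section 3.2).
- Home cycles per participant: 4, cycles 3 to 6 (Study Summary; Section 6.2).
- Scheduled home doses: 20 × 4 = 80, if nobody is replaced.
- Bar: more than 75% (Section 2.2.2).
- Missed-dose rate: not given, so it is varied below.
- The plan does not say which statistic is compared with 75%. The point estimate is assumed.

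**Notation.** S = completed at home, F = moved to the infusion center, U = never given, with S + F + U = 80.
- Rate over scheduled doses = S/80.
- Rate over doses given = S/(80 − U).

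For any S > 0 and U > 0, S/(80 − U) > S/80, so the direction for the crude rate is certain.

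**Size, with 60 completed at home.** Over scheduled doses the rate is 60/80 = 75.0%, which does not exceed the bar.

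| Never given (U) | Moved (F) | Rate over doses given |
|---|---|---|
| 1 | 19 | 60/79 = 75.9% |
| 5 | 15 | 60/75 = 80.0% |
| 10 | 10 | 60/70 = 85.7% |

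**When the crude verdict changes.** The scheduled-dose rate misses the bar when S ≤ 60. The doses-given rate clears it when S > 0.75 × (80 − U) = 60 − 0.75U. Both hold only if 60 − 0.75U < S ≤ 60:
- U = 1: S above 59.25, so 60 only.
- U = 2: S above 58.5, so 59 or 60.
- U = 5: S above 56.25, so 57 to 60.
- U = 10: S above 52.5, so 53 to 60.

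At least 80 − 60 = 20 of the 80 doses must therefore not be completed at home.

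**Scale against sampling error.** A simple 95% interval for 60/80, ignoring clustering, is 0.75 ± 1.96 × √(0.75 × 0.25/80) = 65.5% to 84.5%. Near the bar, one never-given dose moves the rate by about 1 point (75.0% to 75.9%).

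**Model-based rate.** A random-intercept logistic model was fitted to the home cycles alone, without a delivery-mode term, and the rate was averaged over patients. If every patient completes 3 of 4 doses, the estimated patient variance is zero and the model rate equals the crude rate.

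In a clustered example, 12 patients complete all 4 doses and the shortfall lies in the other 8:
- 60 completed: 76.3% of scheduled doses. Over doses given, about 77% with U = 1, 79.0% to 80.6% with U = 5, and 84.4% to 86.2% with U = 10, in several placements of the missed doses. The rate is inflated but the verdict is unchanged.
- 58 completed with U = 5: 74.6% of scheduled doses, against 76.6% to 78.8% of doses given. Here the verdict changes.

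These ranges are not bounds. Placements that concentrate the missed doses in the patients with more completed doses give higher values still.

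**The case against.** The strongest reply is that the definition already settles the matter. It comes first, a dose never given plainly does not meet it, and nothing says that a move to the infusion center is the only failure. Section 11.2 speaks of home cycles, which suggests a per-cycle count. A careful analyst might well choose the scheduled-dose reading. All of that is fair, but no sentence requires that reading, and the sentence that says how adherence is measured points the other way.

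The effect also depends on assumed data. No missed-dose rate is given, the verdict changes only in a narrow band, and one missed dose matters little against the interval. Section 11.2 plans an estimate with an interval and no test against 75%. This limits the importance of the point; the direction of the crude bias stands.

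On the model, the certainty applies to the crude rate. Patient-averaged rates rose in every clustered example tried. A typical-patient estimate (random effect at zero) can slip slightly in some placements, from 89.2% to between 88.3% and 89.1%. Section 11.2 asks for an average rate, which favors the patient-averaged version without specifying it.

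A reader might also infer that participants who stop early fall out of the denominator. The documents do not support that. Section 4.4.2 sends them back to the infusion center, and the failure clause in Section 2.2.2 applies whatever the reason, so together they arguably score those doses as failures already. What the plan does not state is how replaced participants and doses after full study withdrawal are handled.

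**Conclusion.** The point holds as a contradiction within Section 2.2.2 that Section 11.2 does not resolve. Taken literally, the counting rule omits never-given home doses and can only raise the crude adherence rate. With 60 of 80 completed, the rise is from 75.0% to 75.9%, 80.0% or 85.7% for 1, 5 or 10 never-given doses. This assumes no replacements, assumed missed-dose counts, and a point estimate compared with the bar. The crude verdict changes only for 60 − 0.75U < S ≤ 60; elsewhere only the reported rate is inflated. The size of the model-based shift depends on which patients miss doses.

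A reader might go further and conclude that the plan has chosen to exclude missed doses, or that the feasibility conclusion will be wrong. Neither follows. The opening definition points the other way, and the documents give no missed-dose rate from which to judge how likely a changed verdict is. Adherence is a secondary endpoint of a 20-patient pilot, and the primary CTSQ analysis is not touched.

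**What to change.** In Sections 2.2.2 and 11.2, make the unit of count each scheduled home dose (cycles 3 to 6) in place of each dose given. Score a dose not completed at home as a failure, whether it was moved to the infusion center or never given.

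State in advance how medically withheld doses are counted, and likewise the remaining doses of participants who withdraw or are replaced. There is a real trade-off here, because counting all of them mixes treatment persistence with the performance of home delivery. One workable approach is to report the rate with and without them and name which rate is compared with 75%.

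The cost is two or three sentences. Doses administered and visit intervals are already recorded for drug accountability (Section 5.5), and delays and wasted drug in the barriers assessment at Visits 3 to 6 (Section 6.2). The downside is a possibly lower stated adherence rate.

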### **2.2.3 Exploratory**

1. Patient perceptions of home based anti-neoplastic therapy will be measured through semi-structured interviews.
2. Opportunity cost will be measured through the OOCAT survey.

## **3 Study Design**

### **3.1 Characteristics**

Open label, non-randomized trial in patients with multiple myeloma who are receiving DARZALEX FASPRO (daratumumab and hyaluronidase).

### **3.2 Number of Participants**

20

---

### **3.3 Duration of Therapy**

8 months

### **3.4 Duration of Follow Up**

2 months

### **3.5 Treatment Assignment Procedures**

#### **3.5.1 Randomization Procedures (if applicable)**

N/A

#### **3.5.2 Masking Procedures (if applicable)**

N/A

### **3.6 Study Timeline**

#### **3.6.1 Primary Completion**

26 months to complete study enrollment.

#### **3.6.2 Study Completion**

36 months to study completion.

---

## **4 Study Enrollment and Withdrawal**

### **4.1 Eligibility Criteria**

#### **4.1.1 Inclusion Criteria**

Individuals must meet all of the following inclusion criteria in order to be eligible to participate in the study:

1. Able to provide signed and dated informed consent form
2. Willing to comply with all study procedures and be available for the duration of the study
3. Male or female, aged greater than 18 years of age
4. Has a diagnosis of Multiple Myeloma
5. Is on the monthly phase of daratumumab (either IV or SubQ) based regimen (every 4 weeks) (either monotherapy or in combination with oral agents)
6. Is willing to receive daratumumab subcutaneous injections
7. Lives within the range of Jefferson Home Infusion Services

8. Patients are willing to allow home infusion company visit them and administer Darzalex-Faspro in the home.
9. Women of reproductive potential must use highly effective contraception
10. Men of reproductive potential must use highly effective contraception
11. Adequate bone marrow function: ANC >1,000, Platelet Count > 50,000
12. Adequate liver function: AST/ALT < 2.5 times ULN, Bilirubin <2 times ULN
13. Adequate renal function: CrCl ≥ 20mL/min for single agent SC daratumumab. For combination studies: with lenalidomide ≥ 30mL/min
14. English Speaking

#### 4.1.2 **Exclusion Criteria**

An individual who meets any of the following criteria will be excluded from participation in this study:

1. Receiving daratumumab for an indication other than multiple myeloma
2. Receiving daratumumab in combination with other IV or subcutaneous therapy
3. Pregnancy or lactation
4. Known allergic reactions to components of the study product(s)
5. Uncontrolled human immunodeficiency virus (HIV)
6. Seropositive for hepatitis B (defined by a positive test for hepatitis B surface antigen [HBsAg]) who are not on hepatitis B prophylaxis. Subjects with resolved infection (ie, subjects who are HBsAg negative but positive for antibodies to hepatitis B core antigen [anti-HBC] and/or antibodies to hepatitis B surface antigen [anti-HBs]) must be screened using real-time polymerase chain reaction (PCR) measurement of hepatitis B virus (HBV) DNA levels. Those who are PCR positive and not on Hep B prophylaxis will be excluded. EXCEPTION: Subjects with serologic findings suggestive of HBV vaccination (anti-HBs positivity as the only serologic marker) AND a known history of prior HBV vaccination, do not need to be tested for HBV DNA by PCR.
7. Patients with reactivation of hepatitis B will be excluded.
8. Seropositive for hepatitis C (except in the setting of a sustained virologic response [SVR], defined as a viremia at least 12 weeks after completion of antiviral therapy).
9. Chronic obstructive pulmonary disease (COPD) with a forced expiratory volume in 1 second (FEV1) < 50% of predicted normal. Note that FEV1 testing is

required for participants suspected of having COPD and participants must be excluded if FEV1 is < 50% of predicted normal.

10. Moderate or severe persistent asthma within the past 2 years, or uncontrolled asthma of any classification. Note that participants who currently have controlled intermittent asthma or controlled mild persistent asthma are allowed to participate.
11. Clinically significant cardiac disease, including:
  - a. Myocardial infarction within 6 months before randomization, or unstable or uncontrolled disease/condition related to or affecting cardiac function (e.g., unstable angina, congestive heart failure, New York Heart Association Class III-IV)
  - b. Uncontrolled cardiac arrhythmia
  - c. Screening 12-lead ECG showing a baseline QT interval as corrected by Fridericia's formula >470 msec

- Non-English Speaking

